4.1.2 Selection of doses in the trial

The CCK-4 dose selected for this trial reflects standard doses for clinical trials (see [Section 1.2](#)). The administration of 50 µg CCK-4 has been performed in numerous clinical research trials in healthy subjects, elderly subjects, and patients with anxiety disorders. It has proven to be well-tolerated, even in patients with anxiety disorders who are highly sensitive to such challenges [\[P98-0035\]](#), [\[R18-2694\]](#), [\[R18-2695\]](#), [\[R18-2696\]](#).

In this single dose CCK-4 challenge study a higher inhibition of about 90 % (EC90) is intended to be achieved during PSS evaluation in order to ensure adequate target inhibition during the short lasting CCK-4 related stimulus.

4.1.3 Method of assigning subjects to treatment groups

Prior to start of the study, subjects willing to participate will be recruited to cohorts according to their temporal availability. According to the planned sample size, at least 4 cohorts are planned. After assessment of all in- and exclusion criteria, each eligible patient will be randomised to treatment groups in the morning of Day 1 (Visit 2) prior to first administration of trial medication and the appropriate medication number will be assigned. The randomisation will be provided by the sponsor to the trial site in advance.

Once a subject number has been assigned, it cannot be reassigned to any other subject. Subject Numbers are automatically pre-populated via the BRAVE system (during data entry, in an ascending order).

The randomisation procedure is described in [Section 7.6](#).

4.1.4 Drug assignment and administration of doses for each subject

This trial is a 2-way crossover study. All subjects will receive the 2 treatments in randomised order. The treatments to be evaluated are outlined in [Table 4.1.4: 1](#) below.

Table 4.1.4: 1 Dosage and treatment schedule

Treatment	Substance	Formulation	Unit strength	Dosage	Total dose
T (Test)	BI 1358894	Tablet	25 mg	4 tablets (25 mg) q.d for 1 day	100 mg
R (Reference)	Placebo	Tablet	n.a. mg	4 tablets (n.a. mg) q.d for 1 day	n.a. mg

The investigator (or authorised designee) will administer the trial medication as a single oral dose together with about 240 mL of water to subjects who are in a sitting position. For drug administration, the so-called four-eye principle (two-person rule) should be applied. For this, one authorised employee of the trial site should witness the administration of trial medication, and – if applicable – its preparation (e.g. reconstitution), if correct dosage cannot be ensured otherwise.

CCK-4 will be provided in vials containing 50 µg lyophilized CCK-4. Immediately prior to use, 5 mL of sterile normal saline (0.9% NaCl) for injection will be added to the vial containing lyophilized CCK-4 powder and mixed to produce a solution for injection. Before CCK-4 administration, 5 mL (50 µg CCK-4) of the solution is withdrawn from the vial into a syringe. Then the CCK-4 will be administered to the subjects as a bolus injection over 5 seconds (maximum of 8 seconds) via a venous cannula.

In each treatment period, a high-fat, high-calorie meal will be served 30 min before BI drug administration. The subjects must completely consume the meal prior to drug intake. The composition of the standard high-fat, high-calorie meal is detailed in [Table 4.1.4: 2](#); this meal is in compliance with the FDA guidance ‘Food-Effect Bioavailability and Fed Bioequivalence Studies’ [[R03-2269](#)]. For restrictions with regard to diet, see [Section 4.2.2.2](#).

Table 4.1.4: 2

Composition of the high-fat, high-calorie meal

Ingredients	kcal
2 fried eggs (in 15 g butter/margarine) (approximately 100 g)	220
40 g fried bacon ²	151
2 toasted slices of whole-wheat bread	154
15 g margarine for buttering toast slices	112
115 g fried potatoes	130
240 mL whole milk (3.5% fat)	151
Sum¹	918

1 The total caloric content was supplied approximately as following: 156 kcal as protein, 235 kcal as carbohydrate, and 500 to 600 kcal as fat.

2 Vegetarians may replace bacon with 40 g brie 60+ (148 Kcal)

Subjects will be kept under close medical surveillance for 8 days after drug administration as described in the [Flow Chart](#).

During the first 2 h after drug administration, subjects will only be allowed to lie down if supine positioning is required for trial-related measurements (e.g. recording of 12-lead ECG).

The treatments will be separated by a wash-out phase of at least 17 days.

4.1.5 Blinding and procedures for unblinding

The trial is designed double-blind. Neither subject nor investigator will be aware of the trial treatments. The investigator will be supplied with a set of sealed envelopes containing the medication codes. The envelopes will be kept unopened at the study site until the end of data collection or, in an emergency requiring the investigator to know a subject's treatment allocation, opened with appropriate documentation. At the trial close-out visit, all envelopes will be collected.

Access to the randomisation schedule is restricted to the randomisation operators, the Clinical Trial Support group and the Pharmaceutics Department.

Persons directly involved in the conduct of the trial will be blinded to trial treatments. The trial medication will be packed blinded. The trial will only be unblinded after locking of the database, which takes place only after the trial is clinically completed and all queries have been clarified. Access to the randomisation codes will be controlled and documented by a signed confidentiality statement, which will be stored in the TMF.

Regarding the sponsor, the database of this trial will be handled open-label, meaning that the trial functions of the sponsor are unblinded (including clinical monitor, data manager, statistician, bioanalyst, pharmacokineticist, pharmacometrist, drug metabolism scientist as well as dedicated CRO personnel). The objective of the trial is not expected to be affected.

.

4.1.6 Packaging, labelling, and re-supply

4.1.6.1 BI 1358894

Drug supplies will be provided by BI. They will be packaged and labelled in accordance with local law and the principles of Good Manufacturing Practice.

For details of packing and the description of the label, refer to the ISF.

The telephone number of the sponsor and the name, address and telephone number of the trial site are provided in the subject information form. The EudraCT number is indicated on the title page of this protocol as well as on the subject information and informed consent forms.

No re-supply is planned.

4.1.7 Storage conditions

Drug supplies will be kept in their original packaging and in a secure limited access storage area in accordance with the recommended (labelled) storage conditions. If necessary, a temperature log must be maintained to make certain that the drug supplies are stored at the correct temperature. If the storage conditions are found to be outside the specified range, the local clinical monitor (as provided in the list of contacts) is to be contacted immediately.

4.1.8 Drug accountability

The investigator or designee will receive the investigational drugs delivered from the sponsor when the following requirements are fulfilled:

- Approval of the clinical trial protocol by the IRB / ethics committee
- Availability of a signed and dated clinical trial contract between the sponsor and the investigational site
- Approval/notification of the regulatory authority, e.g. competent authority
- Availability of the *curriculum vitae* of the Principal Investigator
- Availability of a signed and dated clinical trial protocol

Only authorised personnel documented in the form 'Trial Staff List' may dispense medication to trial subjects. The trial medication must be administered in the manner specified in the CTP.

The investigator or designee must maintain records of the product's delivery to the trial site, the inventory at the site, the use by each subject, and the disposal of unused products. These records will include dates, quantities, batch / serial numbers, expiry ('use-by') dates, and the unique code numbers assigned to the investigational medicinal product and trial subjects. The investigator or designee will maintain records that document adequately that the subjects were provided the doses specified by the CTP and reconcile all investigational medicinal products received from the sponsor. At the time of disposal of remaining trial medication, the investigator or designee must verify that no remaining supplies are in the investigator's possession.

Proprietary confidential information © 2019 Boehringer Ingelheim International GmbH or one or more of its affiliated companies

All unused medication will be disposed of locally by the trial site upon written authorisation of the trial clinical monitor. Receipt, usage and disposal of trial medication must be documented on the appropriate forms. Account must be given for any discrepancies.

4.2 OTHER TREATMENTS, EMERGENCY PROCEDURES, RESTRICTIONS

4.2.1 Other treatments and emergency procedures

There are no special emergency procedures to be followed. No additional treatment is planned. However, if adverse events require treatment, the investigator can authorise symptomatic therapy. In those cases, subjects will be treated as necessary and, if required, kept under supervision at the trial site or transferred to a hospital until all results of medical evaluations are acceptable.

4.2.2 Restrictions

4.2.2.1 Restrictions regarding concomitant treatment

In principle, no concomitant therapy is allowed. All concomitant or rescue therapies will be recorded (including time of intake on study days) on the appropriate pages of the CRF.

4.2.2.2 Restrictions on diet and life style

While admitted to the trial site, the subjects will be instructed not to consume any foods or drinks other than those provided by the staff. Standardised meals will be served at the times indicated in the [Flow Chart](#). No food is allowed for at least 4 h after drug intake.

From 1 h before drug intake until lunch, fluid intake is restricted to the milk served with breakfast (see [Table 4.1.4: 2](#)), the water administered with the drug, and an additional 240 mL of water at 2 h and 4 h post-dose (mandatory for all subjects). From lunch until 24 h post-dose, total fluid intake is restricted to 3000 mL.

Alcoholic beverages, grapefruits, Seville oranges (sour or bitter oranges) and their juices, and dietary supplements and products containing St. John's wort (*Hypericum perforatum*) are not permitted from 7 days before the first administration of trial medication until after the last PK sample of each study period is collected.

Methylxanthine-containing drinks or foods (such as coffee, tea, cola, energy drinks, or chocolate) are not allowed from 24 h before until 24 h after each administration of trial medication.

Smoking is not allowed during in-house confinement while admitted to the trial site.

Excessive physical activity (such as competitive sport) should be avoided from 7 days before the first administration of trial medication until the end of trial examination.

Direct exposure to the sun or exposure to solarium radiation should be avoided during the entire study.

Proprietary confidential information © 2019 Boehringer Ingelheim International GmbH or one or more of its affiliated companies

4.3 TREATMENT COMPLIANCE

Compliance will be assured by administration of all trial medication in the study centre under supervision of the investigating physician or a designee. The measured plasma and serum concentrations will provide additional confirmation of compliance.

Subjects who are non-compliant (for instance, who do not appear for scheduled visits or violate trial restrictions) may be removed from the trial and the CRF will be completed accordingly (for further procedures, please see [Section 3.3.4.1](#)).

5. ASSESSMENTS

5.1 ASSESSMENT OF EFFICACY

Not applicable.

5.2 ASSESSMENT OF SAFETY

5.2.1 Physical examination

At screening, the medical examination will include demographics, height and body weight, smoking and alcohol history (results not mandatory to be entered into CRF or to be reported), relevant medical history and concomitant therapy, review of inclusion and exclusion criteria, review of vital signs (BP, PR), 12-lead ECG, laboratory tests, a physical examination, and a neurological examination. At the end of trial examination, it will include review of vital signs, 12-lead ECG, laboratory tests, and a physical examination including determination of weight, and a neurological examination.

5.2.2 Vital signs

Systolic and diastolic blood pressures (BP) as well as pulse rate (PR) or heart rate (heart rate is considered to be equal to pulse rate) will be measured by a blood pressure monitor (e.g. Dinamap VC 150,) at the times indicated in the [Flow Chart](#), after subjects have rested for at least 5 min in a supine position. All recordings should be made using the same type of blood pressure recording instrument on the same arm, if possible.

5.2.3 Safety laboratory parameters

For the assessment of laboratory parameters, blood and urine samples will be collected by the trial site at the times indicated in the [Flow Chart](#) after the subjects have fasted for at least 10 h. For retests, at the discretion of the investigator or designee, overnight fasting is not required.

The parameters that will be determined are listed in [Tables 5.2.3: 1](#) and [5.2.3: 2](#). Reference ranges will be provided in the ISF, Section 10.

Manual differential white blood cell count or urine sediment examinations will only be performed if there is an abnormality in the automatic blood cell count or in the urinalysis, respectively.

Proprietary confidential information © 2019 Boehringer Ingelheim International GmbH or one or more of its affiliated companies

Table 5.2.3: 1

Routine laboratory tests

Functional lab group	BI test name [comment/abbreviation]
Haematology	Haematocrit Haemoglobin Red Blood Cell count/Erythrocytes Reticulocyte count White Blood Cells/Leucocytes Platelet Count/Thrombocytes (quant) Neutrophils, eosinophils, basophils, monocytes, lymphocytes
Automatic WBC differential (relative and absolute)	
Manual differential WBC (if automatic differential WBC is abnormal and clinically relevant in the opinion of the investigator), according to local procedures	Polymorphnuclear neutrophils (segs), band neutrophils (stabs), eosinophils, basophils, monocytes, lymphocytes and any abnormalities will be reported
Coagulation	Activated Partial Thromboplastin Time Prothrombin time – INR (International Normalization Ratio) Fibrinogen ESR
Enzymes	AST [Aspartate transaminase] /GOT, SGOT ALT [Alanine transaminase] /GPT, SGPT Alkaline Phosphatase Gamma-Glutamyl Transferase Glutamate Dehydrogenase (GLDH) Creatine Kinase [CK] Creatine Kinase Isoenzyme MB [CK-MB, only if CK is elevated] Lactic Dehydrogenase Lipase Amylase
Hormones	Thyroid Stimulating Hormone ¹ Free T3 - Triiodothyronine ¹ Free T4 - Thyroxine ¹
Substrates	Glucose (Plasma) Creatinine Bilirubin, Total Bilirubin, Direct Protein, Total Protein electrophoresis ¹ Albumin Albumin (Protein Electrophoresis) Alpha-1-Globulin (Protein Electrophoresis) Alpha-2-Globulin (Protein Electrophoresis) Beta-Globulin (Protein Electrophoresis) Gamma-Globulin (Protein Electrophoresis) C-Reactive Protein (Quant) Uric Acid Cholesterol, total Triglyceride Sodium Potassium Chloride Calcium Inorganic phosphate
Electrolytes	

Proprietary confidential information © 2019 Boehringer Ingelheim International GmbH or one or more of its affiliated companies

Table 5.2.3: 1 **Routine laboratory tests (cont).**

Functional lab group	BI test name [comment/abbreviation]
Urinalysis (Stix)	Urine nitrite Urine protein Urine glucose Urine ketone Urobilinogen Urine bilirubin Urine erythrocytes Urine leucocytes Urine pH
Urine sediment (microscopic examination if erythrocytes, leukocytes nitrite or protein are abnormal in urine)	Only positive findings will be reported (for instance, the presence of sediment bacteria, casts in sediment, squamous epithelial cells, erythrocytes, leukocytes)

¹ Protein electrophoresis only at screening. Hormones only at screening and end of trial; for time points of assessment of , refer to [Flow Chart](#).

The tests listed in [Table 5.2.3: 2](#) are exclusionary laboratory tests that may be repeated as required. The results will not be entered in the CRF/database and will not be reported in the CTR. Infectious serology will be performed during screening only. Drug screening will be performed at screening and prior to each treatment period.

Table 5.2.3: 2 **Exclusionary laboratory tests**

Functional lab group	Test name
Drug screening (urine)	Amphetamine/MDA Barbiturates Benzodiazepine Cannabis Cocaine Methadone Methamphetamines/MDMA/XTC Opiates Phencyclidine Tricyclic antidepressants
Infectious serology (blood)	Hepatitis B surface antigen (qualitative) Hepatitis B core antibody (qualitative) Hepatitis C antibodies (qualitative) HIV-1 and HIV-2 antibody (qualitative)

To encourage compliance with alcoholic and drug restrictions, a urine alcohol and drug test (e.g. ADVIA Chemistry XPT system) will be performed prior to each treatment period, and may be repeated at any time during the study at the discretion of an investigator or designee. The results will not be included in the CTR.

The laboratory tests listed in [Tables 5.2.3: 1](#) and [5.2.3: 2](#) will be performed at

Urinanalysis stix and drug screening tests will be performed using e.g. Clinitek Novus test and ADVIA Chemistry XPT system, respectively.

Proprietary confidential information © 2019 Boehringer Ingelheim International GmbH or one or more of its affiliated companies

Laboratory data will be transmitted electronically from the laboratory to the trial site.

5.2.4 Electrocardiogram

5.2.4.1 Twelve-lead ECGs

Twelve-lead ECGs (I, II, III, aVR, aVL, aVF, V1 - V6) will be recorded using a computerised electrocardiograph (e.g. Mortara Eli 250 C) at the times provided in the [Flow Chart](#).

To achieve a stable heart rate at rest and to assure high quality recordings, the site personnel will be instructed to assure a relaxed and quiet environment, so that all subjects are at complete rest.

All ECGs will be recorded for a 10 sec duration after subjects have rested for at least 5 min in a supine position. ECG assessment will always precede all other study procedures scheduled for the same time to avoid compromising ECG quality.

All ECGs will be stored electronically. Electrode placement will be performed according to the method of Wilson, Goldberger and Einthoven.

All locally printed ECGs will be evaluated by the investigator or a designee. Abnormal findings will be reported as AEs (during the trial) or baseline conditions (at screening) if assessed to be clinically relevant by the investigator. Any ECG abnormalities will be carefully monitored and, if necessary, the subject will be removed from the trial and will receive the appropriate medical treatment.

ECGs may be repeated for quality reasons (for instance, due to alternating current artefacts, muscle movements, or electrode dislocation) and the repeated ECG will be used for analysis. Additional (unscheduled) ECGs may be collected by the investigator for safety reasons.

5.2.4.2 Continuous ECG monitoring

Cardiac rhythm (including heart rate) will be monitored by means of continuous 12-lead ECG recording at visit 2 for at least 15 min before CCK-4 challenge until 30 min after the challenge and at visit 3 and 4 for at least 2 h before the BI 1358894 administration (for baseline assessment), and 6 h following drug administration using patient monitors (e.g. Mortara Telemetry System). Abnormal findings will be recorded as AEs if judged clinically relevant by the Investigator but no other data will be transferred to the database.

5.2.5 Other safety parameters

5.2.5.1 Local tolerability

Local tolerability will be assessed by the investigator or designee on the basis of swelling, induration, heat, redness, pain, and other findings.

5.2.5.2 Suicidality assessment

Suicidality assessment to further evaluate the psychological status of the subject will be performed at screening using the Columbia Suicidal Severity Rating scale (C-SSRS). The C

Proprietary confidential information © 2019 Boehringer Ingelheim International GmbH or one or more of its affiliated companies

SSRS is a brief measure which is designed to assess severity and change of suicidality by integrating both, behaviour and ideation. The C-SSRS was designed to address the need for a summary measure to track change in the severity of suicidality across both clinical settings and treatment trials.

The original English version is shown in [Appendix 10.2](#).

5.2.6 Assessment of adverse events

5.2.6.1 Definitions of adverse events

5.2.6.1.1 Adverse event

An adverse event (AE) is defined as any untoward medical occurrence in a patient or clinical investigation subject administered a medicinal product and which does not necessarily have to have a causal relationship with this treatment.

An AE can therefore be any unfavourable and unintended sign (including an abnormal laboratory finding), symptom, or disease temporally associated with the use of a medicinal product, whether or not considered related to the medicinal product.

The following should also be recorded as an AE in the CRF and BI SAE form (if applicable):

- Worsening of the underlying disease or of other pre-existing conditions
- Changes in vital signs, ECG, physical examination, and laboratory test results, if they are judged clinically relevant by the investigator

If such abnormalities already pre-exist prior to trial inclusion, they will be considered as baseline conditions and should be collected in the eCRF only.

The provoked panic symptoms in response to CCK-4 injection (as documented by the PSS score), which are prerequisite for demonstrating a potential effect of the investigational compound, will be considered PD parameters. Since they are an expected and desired response in the context of this trial (even though they constitute an untoward medical occurrence), they will not be recorded as AEs. All other observations not included on the PSS questionnaire occurring during the standard AE reporting time period (see [Section 5.2.6.2.1](#)) are to be documented as AEs.

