Administration of 50 µg CCK-4 was well-tolerated in numerous clinical research trials (see [Section 4.1.2](#)). The CCK-4 related anxiety symptoms show a rapid increase followed by a fast decline within a period of 5 minutes. There may be some residual anxiety symptoms after 10 minutes, but these are usually mild and disappear without any residual symptoms within 30 minutes. Changes in vital signs (blood pressure, pulse rate, respiratory rate) occur during the CCK-4 challenge test. Short lasting changes in pulse rate and blood pressure have been observed together with changes in anxiety-status [[R18-2695](#)].

The panic symptoms induced by CCK-4 may be expressed by the following potential symptoms (all symptoms are covered by the assessment of the Panic Symptom Scale (PSS), vital signs and will be thoroughly monitored):

- Dyspnea
- Dizziness
- Faintness
- Trembling
- Sweating
- Nausea
- Abdominal stress
- Tachycardia
- Chest pain or discomfort

Proprietary confidential information © 2019 Boehringer Ingelheim International GmbH or one or more of its affiliated companies

- Hot flushes
- Anxiety, fear or apprehension
- Fear of dying, losing control, of going crazy

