3.3.4.3 Discontinuation of the trial by the sponsor

Boehringer Ingelheim reserves the right to discontinue the trial at any time for any of the following reasons:

1. Failure to meet expected enrolment goals
2. New toxicological findings, serious adverse events, or any safety information invalidating the earlier positive benefit-risk-assessment. More specifically, the trial will be terminated if more than 50% of the subjects have drug-related and clinically relevant adverse events of moderate or severe intensity, or if at least 1 drug-related serious adverse event is reported
3. Violation of GCP, or the CTP, or the contract with BI, impairing the appropriate conduct of the trial
4. The sponsor decides to discontinue the further development of the investigational product
5. The trial will be stopped if at least 2 subjects show relevant individual QT prolongation (absolute QT or QTc greater than 500 ms), which has been confirmed by a repeat ECG recording
6. Occurrence of severe non-serious adverse events considered as drug-related by the investigator in 2 subjects of the same dose group

The investigator / trial site will be reimbursed for reasonable expenses incurred in case of trial termination (except if item 3 applies).

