5.2.6.1.2 Serious adverse event

A serious adverse event (SAE) is defined as any AE which fulfils at least one of the following criteria:

- Results in death
- Is life-threatening, which refers to an event in which the patient was at risk of death at the time of the event; it does not refer to an event that hypothetically might have caused death if more severe
- Requires inpatient hospitalisation

Proprietary confidential information © 2019 Boehringer Ingelheim International GmbH or one or more of its affiliated companies

- Requires prolongation of existing hospitalisation
- Results in persistent or significant disability or incapacity
- Is a congenital anomaly/birth defect
- Is deemed serious for any other reason if it is an important medical event when based upon appropriate medical judgment which may jeopardise the patient and may require medical or surgical intervention to prevent one of the other outcomes listed in the above definitions. Examples of such events are intensive treatment in an emergency room or at home for allergic bronchospasm, blood dyscrasias or convulsions that do not result in hospitalisation or development of dependency or abuse

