5.2.6.2 Adverse event collection and reporting

5.2.6.2.1 AE collection

Upon enrolment into a trial, the subject's baseline condition is assessed (for instance, by documentation of medical history/concomitant diagnoses), and relevant changes from baseline are noted subsequently.

Subjects will be required to report spontaneously any AEs as well as the time of onset, end time, and intensity of these events. In addition, each subject will be regularly assessed by the medical staff throughout the clinical trial and whenever the investigator deems necessary. As a minimum, subjects will be questioned for AEs (and concomitant therapies) at the time points indicated in the [Flow Chart](#). Assessment will be made using non-specific questions such as 'How do you feel?'. Specific questions will be asked wherever necessary in order to more precisely describe an AE.

A carefully written record of all AEs shall be kept by the investigator in charge of the trial. Records of AEs shall include data on the time of onset, end time, intensity of the event, and any treatment or action required for the event and its outcome.

The following must be collected and documented on the appropriate CRF(s) by the investigator:

- From signing the informed consent onwards until an individual subject's end of trial:

Proprietary confidential information © 2019 Boehringer Ingelheim International GmbH or one or more of its affiliated companies

- All AEs (serious and non-serious) and all AESIs
- The only exception to this rule are AEs (serious and non-serious) and AESIs in Phase I trials in healthy volunteers, when subjects discontinue from the trial due to screening failures prior to administration of any trial medication. In these cases, the subjects' data must be collected at trial site but will not be entered in the CRF or trial database and will not be reported in the CTR.
- After the individual subject's end of trial:
 - The investigator does not need to actively monitor the subject for AEs but should only report any occurrence of cancer and related SAEs and related AESIs of which the investigator may become aware of by any means of communication, e.g. phone call. Those AEs should, however, not be reported in the CRF.

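### The adverse-event exemption for CCK-4-provoked panic symptoms states no time interval and no exception for serious reactions, and its closing sentence is unclear for other PSS-listed symptoms

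*Protocol*

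**What the plan says.** Protocol 5.2.6.1.1 opens with a broad AE definition: "any untoward medical occurrence in a patient or clinical investigation subject administered a medicinal product", with or without a causal link. It then makes one exemption. Its subject is "The provoked panic symptoms in response to CCK-4 injection (as documented by the PSS score"); these are classed as PD parameters because they are expected and wanted in this trial. The protocol accepts that they are untoward, but "they will not be recorded as AEs". The section ends by requiring AE documentation for "All other observations not included on the PSS questionnaire occurring during the standard AE reporting time period".

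The other relevant provisions are:
- **5.2.6.1.2:** "A serious adverse event (SAE) is defined as any AE which fulfils at least one of the following criteria".
- **5.2.6.2.1:** the collection period runs "From signing the informed consent onwards until an individual subject's end of trial", and all AEs, serious or not, are collected in it.
- **5.2.6.2.2:** SAEs and AESIs go to the sponsor within 24 hours.
- **3.3.4.3:** "the trial will be terminated if more than 50% of the subjects have drug-related and clinically relevant adverse events of moderate or severe intensity"; one drug-related SAE, or severe drug-related non-serious AEs in two subjects of a dose group, are also grounds for stopping.
- **1.2.2:** the main CCK-4 response rises and falls within 5 minutes; of residual symptoms after 10 minutes it says that "these are usually mild and disappear without any residual symptoms within 30 minutes".
- **1.4.2.2:** CCK-4 effects are transient, with only 5 minutes given.

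**The concern.** An exemption from AE recording needs a boundary in time and a rule for the case where the expected reaction turns out worse than expected. This one has neither. The challenge is given 5 h after study drug (5.6.2), so it takes place in subjects who have just received a compound in early development.

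An event that is never recorded as an AE gets no seriousness or causality assessment, is not sent to the sponsor as an SAE and is not counted under the AE-based stopping rules. The closing sentence adds a second difficulty. It sorts observations by whether they appear on a questionnaire, not by cause or timing, and the questionnaire lists many ordinary complaints after an oral drug. Staff could apply it differently in good faith, and the AE tables by treatment, a main safety output, would depend on which reading they chose.

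**Working it through.** This is a recording rule with no stated figure to reproduce, so the check sets the provisions side by side.

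**1. Does the exemption carry a time limit?** None is stated in 5.2.6.1.1. The durations in 1.2.2 and 1.4.2.2 are descriptive and the AE rule refers to neither. The reference to documentation by the PSS score does not supply a limit. PSS ratings are due 5, 10, 20 and 30 minutes after injection (5.6.2), but the PSS is also completed at Day 9 discharge and at end of trial (Flow Chart footnotes 11 and 4). A symptom rated at 5 minutes that then persists for hours has still been documented by the PSS.

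**2. Can a provoked reaction become an SAE?**
- 5.2.6.1.1: a provoked symptom is not recorded as an AE.
- 5.2.6.1.2: an SAE is an AE that meets a criterion, for example prolonged hospitalisation.
- 5.2.6.2.2: 24-hour reporting covers SAEs, AESIs and the non-serious AEs relevant to them.
- 3.3.4.3: the AE-based stopping rules count AEs and SAEs.

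The chain breaks at its first link. The sections that might repair it do not clearly do so. Section 5.2.6.2.1 collects all AEs, but the symptom has been taken out of that class. The always-serious list (5.2.6.1.3) is described as a list of further AEs and is not reproduced in the documents. SAP Table 6.1: 1 has a screening phase and on-treatment phases but no challenge phase, and SAP 7.8.1 has no rule for PSS-listed symptoms.

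**3. What does the closing sentence do outside the challenge?** Dizziness, palpitations and nausea are items 2, 5 and 9 of the 18 in Appendix 10.4. Take nausea 2 h after dosing, which is 3 h before the injection:
- *Narrow reading:* it is not a response to CCK-4, so the exemption does not apply and the general AE definition does. It is an AE.
- *Broad reading:* it is on the PSS questionnaire, so the closing sentence does not send it to AE recording.

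The sentence does not exclude such a symptom, but it does not say what to do with it.

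**4. How far apart are the two readings?** This is an illustration only. Dosing to Day 9 discharge is 192 h. The exempt share of that span, if the exemption covers only the expected response, depends on which duration is assumed:
- 5 minutes: (5/60) / 192 = 0.04%
- 30 minutes: 0.5 / 192 = 0.26%

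On the broad reading the share is 100% for all 18 items.

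**The case against.** The strongest reply is that the exemption is limited by cause. It covers symptoms in response to CCK-4, and its stated reason (an expected and desired reaction) does not fit nausea before the injection or dizziness days later. The closing sentence adds observations to AE recording and does not say that PSS items are otherwise excluded. Section 5.2.6.1.4 records nausea as an accompanying symptom of headache AEs, which sits badly with exclusion by name.

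There are also safeguards. Clinically relevant ECG and vital-sign changes remain AEs (5.2.4.2, 5.2.6.1.1). Diagnoses such as syncope or arrhythmia are not PSS items. Provoked scores are kept in the eCRF. The challenge is given in both periods, so the exemption applies under both treatments. The sponsor may also stop on any safety information that overturns the benefit-risk assessment.

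Much of this stands. A reader might infer that drug-caused symptoms escape AE recording throughout the trial because they share a name with a PSS item. The documents do not support that: the causal limit, the general definition and 5.2.6.2.1 all point to recording them. What the reply does not answer is the missing interval and the missing seriousness exception for reactions that CCK-4 did provoke. The ECG and vital-sign safeguards cover only part of the PSS list.

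**Conclusion.** The point holds in two parts. First, as written, a CCK-4-provoked reaction that is prolonged or meets an SAE criterion has no stated route to SAE recording, 24-hour reporting or the AE-based stopping rules. This follows from the text and needs no assumption about frequency. Second, the closing sentence is ambiguous for PSS-listed symptoms that CCK-4 did not provoke. The better reading is that they are AEs, but the sentence can be misread.

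A reader might go further and infer that lost events would conceal a crossing of the more-than-50% stopping rule. The documents give no expected frequency, intensity or misclassification rate for such symptoms, so they do not support that inference or any estimate of the bias in the AE tables. The primary endpoint, its analysis and the sample size are untouched. The point should be corrected because it bears on subject safety and the correction is short.

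**What to change.** Reword the exemption in 5.2.6.1.1 so that:

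1. It covers only PSS-listed symptoms with onset after a CCK-4 injection and within a stated post-injection interval. The sponsor sets the length after reconciling the 5-minute statement in 1.4.2.2 with the 30-minute statement on residual symptoms in 1.2.2. Neither can be adopted as the protocol's settled figure, since 1.2.2 says only what usually happens.
2. PSS-listed symptoms that start before the injection, start or continue beyond the interval, or are not attributed to CCK-4 are recorded as AEs.
3. Any event meeting a criterion in 5.2.6.1.2 is recorded and reported as an SAE, whether or not it is a PSS item.

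The cost is a few sentences of protocol text and site training. The downside is that a few more AEs will be recorded.
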